ABSOLUTE BIOAVAILABILITY/PHARMACOKINETIC AND RESIDUAL DRUG ANALYSIS OF DURAGESIC® TRANSDERMAL SYSTEM AND GENERIC FENTANYL TRANSDERMAL SYSTEM IN HEALTHY ADULTS

Short title: Fentanyl Patch Pharmacokinetics in Healthy Adults

U01 Principal Investigator:

[name] (contact), PhD, RPh

Medically Accountable Investigator:

[name], MS

Sponsor:

Food and Drug Administration

NCT02531971

Version 13.0

01 February 2018

STATEMENT OF COMPLIANCE

This study will be conducted in compliance with the protocol, International Conference on Harmonisation Good Clinical Practice E6 (ICH-GCP) and the applicable Food and Drug Administration and other Department of Health and Human Services regulatory requirements.

All key personnel (all individuals responsible for the design and conduct of this study) have completed Human Subjects Protection Training.

PROTOCOL SUMMARY

Title:	Absolute Bioavailability/Pharmacokinetic and Residual Drug Analysis of Duragesic® Transdermal System and Generic Fentanyl Transdermal System in Healthy Adults
Population:	Healthy, non-smoking adults age 18-45 years
Number of Sites:	Single site: University of Maryland School of Medicine/General Clinical Research Center (GCRC)
Study Duration:	Approximately up to 18 months
Subject Participation Duration:	Approximately 12-18 weeks including the screening Session
Description of Study Products:	Fentanyl citrate injection, Fentanyl Duragesic®, matrix type, Janssen Pharmaceuticals transdermal drug delivery system (TDDS); Mylan (fentanyl) matrix type, Mylan Pharmaceuticals TDDS; naltrexone hydrochloride oral tablets and naloxone hydrochloride injections
Objective:	To determine serum fentanyl levels after using reference (Duragesic®) and generic fentanyl (Mylan) TDDS, and comparing them to the serum levels of intravenous fentanyl citrate, in healthy adult subjects
Description of Study Design:	This will be a three treatment, open-label, randomized, crossover clinical study with a Run-In Study Session (Study Session I) of intravenous fentanyl citrate, followed by a transdermal administration of a single strength of the reference listed drug (RLD) Duragesic®, and a transdermal administration of a generic equivalent to the RLD, Mylan fentanyl TDDS. A total of 24 subjects will be enrolled to complete this study.
	A) Pharmacokinetic Determination of Strength
	The study will be a three treatment, open-label, randomized crossover study, with a Run-In Study

Session I of an intravenous fentanyl citrate administration, with at least a one week washout interval between Study Sessions.

The study products are:

- Single intravenous (100 µg) administration of fentanyl citrate (50 µg/mL)
- Duragesic® TDDS containing fentanyl (25 µg/h) to be worn for 3 days (72h)
- Mylan fentanyl TDDS (Generic) containing fentanyl (25 µg/h) to be worn for 3 days (72h)

Each Subject will be his/her own control.

Administration of naloxone injection will be used to test for withdrawal prior to using any study products, and to be used emergently in case of fentanyl toxicity. Naltrexone oral tablets will be used to block the opioid receptors to avoid any clinical effects or side-effects of fentanyl.

Blood samples will be obtained as follows (based on administration route):

- 60 min pre-IV administration and then up to 36 hr (1.5 days) post start of IV administration
- 60 min pre-application and then up to 192 hr (8 days), during 3 day wear and post removal of RLD
- 60 min pre-application and then up to 192 hr (8 days), during 3 day wear and post removal of Generic product

B) Residual Drug Analysis determination of Strength

In conjunction with the above described study residual drug analysis will also be conducted for the used RLD and Generic TDDS described in Part A.

- Prior to administration to the Subject as described in Part A, the TDDS will be weighed and the weight recorded.
- The pouch, release liner and all items coming into contact with the TDDS (gloves, forceps, etc.) to be applied in Part A will be retained for analysis.
- The used TDDS will be retained for drug content analysis.
- Upon removal of the product after prescribed wear Session, the skin (at site of application) will be swabbed and the swab retained for drug content analysis.
- All items coming into contact with the TDDS during removal from the Subject and storage in a separate labeled sealable foil pouch for analytical retention will be analyzed for drug content.

2 BACKGROUND INFORMATION AND SCIENTIFIC RATIONALE

2.1 Background Information

There are numerous transdermal drug delivery systems (TDDS) that are currently available in the United States, the first of which was approved by the Food and Drug Administration (FDA) in 1979 [1]. Transdermal drug delivery systems (TDDS) available in the form of patches are convenient, attractive, and easy to use systems. Fentanyl is a very popular TDDS available on the United States market today. Drug release from these TDDS varies significantly and is dependent on a number of factors including system design, physicochemical properties of the drug, excipients, occlusion, sweat, skin condition, skin type and temperature. Investigating the influence of these factors on drug release from reference and generic products that are often available in different forms is important to ensure that generic products are not less safe than the reference product. Accurate determination of the rate and extent of drug release and absorption is crucial to ensure the safety of individuals using this and other types of TDDS.

Positive outcome of this project will identify appropriate methods to determine the rate and extent of drug release and absorption from TDDS, and will help regulatory agencies in the development of Guidances for Industry regarding the characterization of drug release and absorption kinetics to ensure the safety of individuals utilizing these types of products.

2.2 Rationale

The rationale of this study is to determine the delivery rate and the extent of absorption of fentanyl drug release from FDA-approved TDDS products (reference e.g. Duragesic®, versus Mylan transdermal patches) that have different inactive ingredients. can be determined in humans by accurately quantifying residual drug from TDDS post-wear, and the delivery rate can be determined in pharmacokinetic studies. This study will compare fentanyl levels by using in vitro skin flux permeation studies, as a predictor of in-vivo bioequivalence and pharmacokinetics of Duragesic® and Mylan fentanyl TDDS. This will be done through development of an appropriately controlled and well-characterized in-vitro methodology to quantify the in-vivo exposure of healthy adults to fentanyl during TDDS wear, so that the rate of drug delivery can be defined in a manner that can help the regulatory agency (FDA) in developing Guidance for Industry regarding the characterization of drug release and absorption kinetics to ensure the safety of individuals utilizing these types of products.

In the clinical study component, we will employ two types of evaluation to determine the rate and extent of drug release and absorption from fentanyl TDDS, namely residual drug analysis post-wear and pharmacokinetic analysis in healthy adult Subjects. In addition, we will compare the serum drug concentrations following TDDS and intravenous administration, in

order to explore bioequivalence of these TDDSs. We will conduct residual drug analysis of TDDS following in vivo wear using highly sensitive validated quantification methods.

Duragesic® versus Mylan (fentanyl) TDDS

	Duragesic®	Mylan (fentanyl) TDDS
Inactive ingredients	polyester/ethyl vinyl acetate, polyacrylate adhesive	dimethicone NF, polyolefin film backing, silicone adhesive
TDDS type	Matrix	Matrix
Manufacturer	Janssen	Mylan

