3.2 Study Outcome Measures

The main outcome measure of the study is the determination of the pharmacokinetic parameters of fentanyl in healthy adult Subjects (i.e., clearance (CL), volume of distribution (V), elimination rate constant (Kel), maximum serum concentration (Cmax); time of maximum serum concentration (Tmax) of fentanyl and area under the serum concentration-time curve (AUC). In addition, we will determine residual drug content from worn Duragesic® and Mylan fentanyl TDDS to estimate total amount of absorbed fentanyl from each.

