8.3 Final Analysis Plan

The primary statistical analysis will be performed on the natural log transformed AUC_{0-t} , AUC_{0-A} and C_{max} of Fentanyl from the three Study Sessions using SAS V 9.3. A linear mixed effects model will be used to assess the effects of treatment, Session, sequence and Subject within sequence on natural log transformed AUC_{0-t} , AUC_{0-C} and C_{max} . The treatment, Session, sequence effect will be treated as fixed effects and assessed at a significance level of 0.05. The Subject within sequence will be treated as a random effect. Intra and inter individual variabilities will be obtained. The least square mean estimates for the adjusted differences between treatment means (the log transformed AUC_{0-t} , AUC_{0-C} and C_{max}) and the standard error associated with these differences will be obtained. The geometric means for AUC_{0-a} will be obtained by exponentiating the log transformed AUC_{0-i} for all the three treatments to determine the absolute bioavailability.

The absolute bioavailability for Duragesic® TDDS and Mylan fentanyl TDDS will be calculated.

The analyses for IV administration of fentanyl citrate will be as follows:

Non compartmental and compartmental analyses will be conducted to estimate the PK parameters such as clearance, volume of distribution, elimination rate constant, maximum serum concentration; time of maximum serum concentration and area under the serum concentration-time curve. All analyses will be conducted using Phoenix® WinNonlin® 6.3 (Pharsight, a Certara Company, CA). Absolute bioavailability will be calculated.

The analyses for both TDDS applications (Duragesic® and Mylan fentanyl) will be as follows:

The serum fentanyl concentrations will be determined and the PK parameters such as C_{max} , T_{max} , AUC, steady concentrations (C_{ss}) of fentanyl in each Subject will be elucidated. The rate of fentanyl absorption in each Subject is calculated by dividing the C_{ss} by the clearance predicted from the IV bolus data.

Cumulative amount of fentanyl released by Duragesic® at the end of study Session will be obtained by subtracting residual fentanyl still remaining in the TDDS at the end of the study Session from the total amount of the drug present in an unused TDDS.

Similarly, cumulative amount of the drug released by the Mylan TDDS at the end of study Session is computed.

The rate of drug release from Duragesic® and Mylan TDDS will be determined.

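### Residual and PK delivery are measured on the same worn patches, but section 8.3 states no PK absorbed amount, misstates the PK rate, leaves the bioavailability dose undefined and never compares the two methods within subject

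*Combined protocol and SAP*

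**What the plan says.** **Purpose.** Section 2.1 says that a positive outcome of the project "will identify appropriate methods to determine the rate and extent of drug release and absorption from TDDS". Section 2.2 says of the clinical component that "we will employ two types of evaluation to determine the rate and extent of drug release and absorption from fentanyl TDDS", and names them as post-wear residual analysis and PK analysis. The Protocol Summary heads both Part A (PK) and Part B (residual) as determinations of strength. Part B states: "In conjunction with the above described study residual drug analysis will also be conducted for the used RLD and Generic TDDS described in Part A". Each subject also has an IV run-in session.

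**Residual side of 8.3.** Cumulative release comes from "subtracting residual fentanyl still remaining in the TDDS at the end of the study Session from the total amount of the drug present", where the starting content is that of a patch not yet worn. Section 3.2 says residual content is used "to estimate total amount of absorbed fentanyl from each". Section 8.3 adds "The rate of drug release from Duragesic® and Mylan TDDS will be determined", with no formula.

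**PK side of 8.3.** The plan lists Cmax, Tmax, AUC and Css for the patches. It then states: "The rate of fentanyl absorption in each Subject is calculated by dividing the C_{ss} by the clearance predicted from the IV bolus data". It also states "The absolute bioavailability for Duragesic® TDDS and Mylan fentanyl TDDS will be calculated", with geometric means described by treatment. No bioavailability formula and no patch dose are given. Section 8.2.1 lists AUC0-infinity for both patches.

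**Comparisons.** Section 8.1 and the mixed model in 8.3 compare products or treatments. The closing t-test in 8.3 concerns release-rate means. It does not say which means are compared or whether the test is paired, and it does not mention PK-derived rates.

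**The concern.** Two methods are applied to one patch in one subject, and both are described as measuring rate and extent of delivery. The analysis plan never puts them on a common scale or sets one against the other.

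This matters because residual analysis measures drug that has left the patch, whereas section 3.2 treats it as drug absorbed. The Protocol Summary keeps the skin swab, release liner and contact items for drug analysis, so it recognises that drug can leave the patch without being absorbed. Section 2.2 shows that the two products have different adhesives and backings, so the gap could differ between them. If one method showed a product difference and the other did not, the planned tables would give no prespecified way to interpret it. Choosing afterwards which method to believe would be open to the charge that the result drove the choice.

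**Working it through.** The documents state no figure for agreement between methods, so there is none to reproduce. The checks are on units, definitions, feasibility and precision.

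**1. The PK rate as written.** Css is in µg/L and CL in L/h.
- Css / CL: (µg/L) / (L/h) = µg·h/L², which is not a rate.
- Css × CL: (µg/L) × (L/h) = µg/h, which is a rate.

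As an illustration, take a true input of 25 µg/h (the nominal rate). The documents give no clearance, so the values below are assumed.

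| Assumed CL (L/h) | Css = 25/CL (µg/L) | Css / CL | Css × CL (µg/h) |
|---|---|---|---|
| 30 | 0.833 | 0.028 | 25 |
| 50 | 0.500 | 0.010 | 25 |
| 80 | 0.313 | 0.0039 | 25 |

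As written, the figure falls with the square of clearance at a fixed input. It cannot be set beside a residual release rate.

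**2. The PK amount that could be stated.** A_PK = CL_IV × AUC0-infinity(patch) = IV dose × AUC0-infinity(patch) / AUC0-infinity(IV). Both ingredients are planned: CL in the IV part of 8.3 and patch AUC0-infinity in 8.2.1. The result is in µg, like the residual amount A_res. The nominal scale is 25 µg/h × 72 h = 1800 µg.

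**3. What bioavailability would mean.** F = A_PK / patch dose. Three readings of the dose are open:
- residual-derived release: F = A_PK / A_res, the inverse of the residual/PK ratio;
- nominal delivery: F = A_PK / 1800 µg;
- unused patch content: F = A_PK / content.

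These are different quantities, and 8.3 does not say which is meant.

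**4. Sampling windows**, using the 24 h half-life in section 4.
- Patch: 192 − 72 = 120 h after removal, or 120/24 = 5 half-lives.
- IV: 36/24 = 1.5 half-lives. A single-exponential terminal phase would still be at 0.5^1.5 = 0.35 of its starting level. This is not 35% of the total IV AUC, but the extrapolated part and the terminal slope rest on a short window. Any resulting error in CL may go the same way in every subject.

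**5. What cancels.** For products D (Duragesic) and M (Mylan) in one subject:

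log(A_res,D / A_PK,D) − log(A_res,M / A_PK,M) = log(A_res,D / A_res,M) − log(AUC_D / AUC_M).

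The same CL_IV enters both A_PK terms and drops out. The contrast therefore asks whether the two methods give the same product ratio, and it does not depend on the IV estimate. A true change in clearance between Sessions II and III does not cancel; it goes into the residual error.

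**6. Precision.** n = 24 from the Protocol Summary. The documents give no SD, so the SD of the log ratio is assumed. For one product's geometric mean ratio, the 95% half-width on the log scale is t(0.975, 23) × SD / √24, with t = 2.069 and √24 = 4.899.

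| Assumed SD | Half-width | 95% CI: times or divided by |
|---|---|---|
| 0.15 | 0.063 | 1.065 |
| 0.20 | 0.084 | 1.088 |
| 0.30 | 0.127 | 1.135 |
| 0.40 | 0.169 | 1.184 |
| 0.50 | 0.211 | 1.235 |

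For the between-product contrast with 12 subjects per sequence, the formula is the same, with 22 degrees of freedom (t = 2.074) and the SD of the within-subject difference in log ratios. Over the same assumed range the factor runs from 1.066 to 1.236.

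**The case against.** **Method comparison is not an objective.** Section 3.1 lists bioequivalence and bioavailability, release rate between products, and residual content. Section 3.2 lists no agreement outcome, and the aim in 2.1 belongs to a project that also includes in vitro work. This stands. A reader might infer that the trial leaves a formal objective unanalysed; the documents do not support that.

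**The methods may be meant to complement each other.** Another sentence in 2.2, whose grammatical subject is missing, can be read as taking extent from residual drug and delivery rate from PK. Section 8.3 roughly follows that split. This is a fair reading, but the sentence naming the two evaluations assigns rate and extent to both jointly, and the Summary heads both parts as determinations of strength. Even on the complementary reading, the PK rate is in the wrong units.

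**PK extent is not absent.** Absolute bioavailability is a PK measure of extent, and an amount is one multiplication away. A reader might infer that the plan has no PK extent measure, or that the trial could never say whether residual analysis over- or under-states delivery. Neither follows. If the dose in F were the residual-derived release, F would itself relate the two methods. The gap is that the dose is undefined and the calculation is described by treatment, not as a per-subject ratio.

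**The within-product ratio may be biased.** This stands. With IV sampling ending at 36 h, a ratio away from 1 could not be attributed to residual analysis alone.

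**No data are lost.** This also stands. Both data sets are collected and analysed; only the pairing is unused.

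**Conclusion.** The point holds as a gap between the rationale and section 8. The formula for the PK absorption rate is dimensionally wrong, the patch dose for bioavailability is undefined, no PK absorbed amount is stated, and no within-subject comparison of methods is specified. It is a worthwhile, inexpensive improvement and does not undermine the planned product comparison of AUC0-t and Cmax.

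No loss can be quantified. The CI factors of 1.065 to 1.235 describe how precise the added analysis would be. They rest on 24 complete pairs and an assumed log-ratio SD of 0.15 to 0.50. The between-product contrast is the sound part, since it is free of error in the IV clearance estimate. The conclusion is confined to section 8, because section 7 was not in the text reviewed.

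**What to change.** Amend section 8.3 as follows.

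1. Write the absorption rate as Css × CL, and give the formula for the residual-derived release rate.
2. For each subject and patch, compute the PK absorbed amount as IV CL × patch AUC0-infinity, and the residual-derived amount. State whether drug found on swabs, liners and contact items is subtracted from the latter.
3. Define the patch dose used for absolute bioavailability.
4. Make the main method comparison the between-product contrast of the log residual/PK ratio in the two-session crossover model, with product, session and sequence as fixed effects and subject within sequence as random. Report it with a 95% CI.
5. Report each product's geometric mean ratio with 95% CI, labelled exploratory, and note that IV sampling ends at about 1.5 of the stated half-lives.

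The cost is SAP wording and one more table; no new samples or visits are needed. The downside is that the within-product ratios may share a systematic error from IV clearance and could be over-read, hence the exploratory label.

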3 OBJECTIVES

3.1 Study Objectives

The objectives of this open label, randomized, crossover study are to

- To explore bioequivalence of Duragesic® transdermal system and generic Mylan fentanyl TDDS, and compare bioavailability to direct IV infusion of fentanyl citrate.
- To conduct release rate analysis of generic fentanyl (Mylan) TDDS compared to Duragesic® TDDS.
- To determine the residual drug content of the Duragesic® and generic fentanyl TDDS.

3.2 Study Outcome Measures

The main outcome measure of the study is the determination of the pharmacokinetic parameters of fentanyl in healthy adult Subjects (i.e., clearance (CL), volume of distribution (V), elimination rate constant (Kel), maximum serum concentration (Cmax); time of maximum serum concentration (Tmax) of fentanyl and area under the serum concentration-time curve (AUC). In addition, we will determine residual drug content from worn Duragesic® and Mylan fentanyl TDDS to estimate total amount of absorbed fentanyl from each.

4 STUDY DESIGN

This is a three treatment open-label, randomized cross-over clinical study with a Run-In Study Session I of intravenous fentanyl citrate, followed by randomization to Duragesic® and generic fentanyl in a sequential, 2-Session fashion with at least a one week wash-out Session between the sessions.

The study design is shown below:

Study Session I (Run-in)	Randomization		Study Session II	Study Session III
Intravenous -Fentanyl		Study Arm 1	Duragesic®	Mylan Fentanyl
		Study Arm 2	Mylan Fentanyl	Duragesic®

The study will consist of a total of twenty-five Study Days (24 Subjects) within three Study Sessions, with at least a one week washout Session between successive Study Sessions. The half-life of fentanyl is approximately 24 hours. Hence, 5 days (i.e. 5 half-lives) will be sufficient for >95% of fentanyl to be eliminated from the body. Each of the 24 Subjects will be enrolled to complete all twenty-five study days (Run-In Study Session I = 5 Study Days; Study Sessions II and III = 10 Study Days each). The study is open label and not blinded, because PK assessment is not subject to participant and/or observer bias. After each Study Session is completed, the available safety data will be reviewed by an Independent Safety Monitor (ISM) to determine whether or not to proceed to the next Study Session.

Considering the objective of the study to explore bioequivalence of Duragesic® and generic fentanyl and to conduct release rate analysis of generic fentanyl to Duragesic®, the above study design would adequately address both questions. The randomization to sequences [Reference (R) –Test (T), T-R] would appropriately take into account the sequence and the Session effect for bioequivalence evaluations. Having all Subjects enter the intravenous Run-In Study Session I initially would also help in accurate determination of absolute bioavailability for Duragesic® and generic Mylan fentanyl in this study.

Each Subject will be his/her own control and each Subject will sign an institutional review board-approved consent form explaining the purpose, nature, risks, benefits, and duration of the study. The study will be conducted in accordance with good clinical practice guidelines and with the ethical principles originating in the Declaration of Helsinki.

The three Study Sessions are as follows:

Study Session I (Run-in):

Each of the 24 Subjects will start the study with the Run-In Session of intravenous fentanyl citrate infusion by giving a single-dose of 100 µg fentanyl citrate infusion (2 mL over 2 minutes) as described in the Manual of Procedures. Each Subject will receive a naltrexone hydrochloride 50 mg oral tablet 12-17 hours ± 1 hour before and again shortly prior to intravenous administration and then as described below after intravenous administration for 7 additional doses, for a total of nine 50 mg oral doses of naltrexone hydrochloride tablets.

Study Session II:

Twelve Subjects will be randomized to Study Arm 1 which will receive the Duragesic® fentanyl TDDS (25 µg/h); and other 12 Subjects to Study Arm 2 which will receive the Mylan fentanyl TDDS (25 µg/h). The patches will be applied for 3 days on each Subject. The Subject's skin in the area of application (upper arm region) will be relatively free of hair before TDDS application. Each Subject will receive a naltrexone hydrochloride 50 mg oral tablet 12-17 hours ± 1 hour before and again shortly prior to patch application and then as described below after patch application for 16 additional doses, for a total of eighteen 50 mg oral doses of naltrexone hydrochloride tablets.

Study Session III:

The 12 Subjects who were randomized to Study Arm 1 to receive the Duragesic® fentanyl TDDS (25 µg/h) will cross-over to receive the Mylan fentanyl TDDS (25 µg/h) applied; and the other 12 Subjects who were randomized to Study Arm 2 to receive the Mylan fentanyl TDDS (25 µg/h) will now cross-over to receive the Duragesic® fentanyl TDDS (25 µg/h). The patches will be applied for 3 days on each Subject. Each Subject will receive a naltrexone hydrochloride 50 mg oral tablet 12-17 hours ± 1 hour before and again shortly prior to patch application and then as described below after patch application for 16 additional doses, for a total of eighteen 50 mg oral doses of naltrexone tablets.

